Randomize Eligible Hospitalized Patients (Open Label, Parallel Efficacy, Active Control Standard of Care (SOC), Two Arm Study) Selected Ayurveda Formulation (Adjuvant) Versus SOC (Active Control) Time Points Clinical Assessment Investigations Case Record Form (CRF), Medical Diagnostic (PCR), Serology (IgM, IgG), History Clinical Examination, Ayurveda Baseline Routine Hematology Profile, Special Assessment, Health Status (WHOQs), Assays, X-Ray Chest & Imaging, ECG QoL (HR-BHF) Brief Clin Exam, Ayu Exam, Health Diagnostic (PCR), Serology (IgM, IgG), Week 4 Routine haematology Body Profile, Status (WHO-Qs) & QoL (HR-BHF Qs), Adverse Events (AEs) Special Assays Brief Clin Exam, Ayu Exam, Health Diagnostic (PCR), Serology (IgM, IgG), Week 8 Status (WHO-Qs) & QoL (HR-BHF Routine haematology Body Profile, Qs), Adverse Events (AEs) Special Assays Completion Outcome Assessment, CRF Diagnostic (PCR), Serology (IgM, IgG), Week 12 Clin Exam, Ayu Exam, WHO- Qs & Routine haematology Body Profile, QoL (HR-BHF Qs), AEs Special Assays

*Further Assessment Time Points: (i) During Hospitalization: Daily monitored vital parameters, disease symptoms, disease progression and recovery, and investigations carried out as per protocol till DISCHARGE; Laboratory and Imaging investigations as per protocol but the study investigator and treating physician can do any additional test as per their judgment (ii)Post DISCHARGE: Daily Telephonic Contact using a special mobile phone application for any relapse or any other symptoms or complications or any other Issue (iii) Discharge: Complete all formalities as required for study completion (iv) Skip week 4 or week 8 end point evaluation within 2 weeks of DISCHARGE

The total study period is 12 weeks; Primary Efficacy is 'Clinical Recovery' as described in the protocol; Study participant developing severe COVID 19 or severe complication and requiring special critical support/ ICU/ ventilator support will be withdrawn from the study but followed up to record outcome;

Both Ayurvedic and Allopathic Physicians will jointly examine and monitor study participants in addition to the hospital treating physician

Fig 1: Study Flow Diagram with Schedule of Important Study Events

i. Eligibility:

A) Inclusion Criteria:

- i. Typical clinical presentation of acute onset febrile illness with cough and a RT_PCR based laboratory confirmation test for COVID-19
- ii. Patients with either sex, 18 to 75 years age

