- iii. Patients with mild to moderate patients
- iv. All patients must agree not to share medication
- v. Patients willing to participate and sign an informed consent

B) Exclusion Criteria:

- i. Patients suffering from severe COVID-19 Disease as judged by a physician and fulfilling at least two of the following three criteria* (i) Respiratory distress at room ambience (≥30 breaths per min) (ii) Oxygen saturation at rest ≤93% (peripheral digital arterial oxymetry) and requiring oxygen support for over one hour to normalize (iii) Any of the known COVID-19 complications and emergency procedures which may require shift/admission in intensive care unit such as respiratory failure, adult respiratory distress syndrome, requirement of oxygen support for over 1 hour, requirement of mechanical ventilation, septic shock, or severe non-respiratory organ dysfunction or failure. (Adapted and modified from the reference: Yang Liu et al. Lancet Infect Dis 2020, 2020 https://doi.org/10.1016/S1473-3099(20)30232-2)
- ii. Chronic, Severe, Unstable, Uncontrolled co-existent medical illness such as Diabetes, Hypertension, Cardiac disorders, liver, kidney disorders and lung disorders or other disease of concern which may put the patient at increased risk during the study
- iii. History of immunosuppression: solid organ or bone marrow transplant, use of immunosuppressive antimetabolic and biologic agents, intrinsic immunodeficiencies, HIV infection.
- iv. Active cancer diagnosis, on palliative treatment or requiring current therapy with antimetabolic agents, immunotherapy or radiotherapy.
- v. Patients on parenteral nutrition
- vi. Patients with known sensitivity or contraindication to any of the ingredients of study medication
- vii. History of bleeding haemorrhoids, haemoptysis, acid peptic diseases, ulcers and pulmonary diseases (tuberculosis, asthma, etc.)
- Patients who are likely to worsen or planed ICU admission or ventilator support due to any reason

- ix. Pregnancy and lactation
- x. Participation in a drug interventional clinical drug trial of any nature in the three month period preceding onset of COVID-19
- xi. Participation in any other clinical trial of an experimental agent treatment for COVID-19
- xii. Patients on any kind of Ayurveda treatment or any other alternative and complementary medicinal systems such as Homeopathy, Unani, Siddha and in particular requiring oral therapy of any kind.

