- xiii. Physician decision that involvement in the study is not in the patient's best interest

j. Efficacy:

A) Primary Outcomes:

- a) Mean time (days) for clinical recovery [Day of randomization to the day of clinical recovery (see criteria below)]
- b) Proportion of patients showing 'clinical recovery'

Criteria of 'Clinical Recovery':

- i. Normal body temperature (≤36.6°C axilla or ≤37.2 °C oral)
- ii. Absence of cough or mild cough (infrequent, short episodic, non-wheezy, relieved by minimal or no medication, not interfering with routine speech and not related to lying in bed, mild sore throat or nasal congestion)
- iii. Absence of breathlessness on routine daily self-care chore or respiratory rate less than 30 breaths per minute without supplemental oxygen
- iv. Absence of any other symptom/sign attributed to COVID-19 illness
- v. Normalization of SpO2 by standard peripheral oximetry device (above 95 percent)
- vi. Recovery should be sustained for at least 48 hours under physician observation
- vii. Assessed by physician blinded to treatment allocation (blinded end-point assessment)
- viii. All of the above criteria ought to be fulfilled

Note: Clinical recovery would be deemed from the first day of satisfying the above criteria

B) Secondary Outcomes:

- 1) Rate of patients with negative SARS-CoV-2 on nasal or throat swab in a 2 day continuous real time RT-PCR test beginning from 'first day of clinical recovery' or 'Day 10 after onset of symptoms depending on whichever of the two time points is first achieved
- 2) Timelines (days counted from onset of illness)- normal body temperature, absence or minimal cough (see 'clinical recovery' for the definition), absence of dyspnoea, onset of clinical pneumonia, pneumonia diagnosed on chest X-Ray or CT scan, time to supplemental

oxygen, admit in intensive care unit, mechanical ventilation (non-invasive), mechanical ventilation (invasive), steroid use, respiratory failure, adult respiratory distress syndrome, cytokine storm syndrome, secondary infection, shock, septicaemia shock, hospital discharge, negative nose or throat swab confirmatory test, and all-cause mortality.

- 3) Proportion of patients developing an event that reflects clinical or otherwise improvement of worsening (the events are similar to those listed under Timelines, see above)
- 4) Improvement on pulmonary function tests using simple 'home expiratory spirometer' device and peripheral pulse oximetry

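### A patient who is still breathless can be declared clinically recovered, because criterion iii joins its two parts with 'or'

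*Protocol*

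**What the plan says.** The adjunct-treatment Protocol has two primary outcomes (section j, Efficacy, A): mean time from randomization to clinical recovery, and the proportion of patients who recover. Both rest on one list of criteria. Criterion iii is the only item that names breathlessness: "Absence of breathlessness on routine daily self-care chore or respiratory rate less than 30 breaths per minute without supplemental oxygen".

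The other items are normal temperature (i), no cough or mild cough (ii), "Absence of any other symptom/sign attributed to COVID-19 illness" (iv), "Normalization of SpO2 by standard peripheral oximetry device (above 95 percent" (v), persistence for 48 hours under observation (vi) and assessment by a blinded physician (vii). Item viii requires all of them together. Recovery is dated from the first day on which the criteria are satisfied.

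Section i (Eligibility) limits entry to mild to moderate disease. It excludes "Patients suffering from severe COVID-19 Disease as judged by a physician and fulfilling at least two of the following three criteria", the first of which is "Respiratory distress at room ambience (≥30 breaths per min".

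Absence of dyspnoea appears separately among the timelines in the secondary outcomes of section j.

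**The concern.** A criterion on breathing in a recovery definition would be expected to require that breathlessness has gone. This one offers a way round: a rate below 30 off oxygen is sufficient by itself. That limit marks the boundary of what the Protocol regards as severe, and the trial sets out to enrol patients below it. Meeting it shows that the patient is not in the severe range for that sign. It does not show recovery from mild or moderate illness.

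Both primary outcomes are at stake. The time outcome is dated too early whenever breathlessness outlasts the other criteria. The proportion outcome is affected only if breathlessness never resolves during observation. An early date can also carry into secondary outcome 1, where swab timing may start from the first day of recovery. In a multicentre trial there is a further risk of inconsistency: some assessors may follow the text, while others may read breathlessness into criterion iv.

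**Working it through.** The plan has no figure to reproduce here. The 70 per arm is stated to be a convenience size (section n), and no calculation involves the recovery definition. The check is therefore one of logic.

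**Step 1: when is criterion iii met?** The phrase on supplemental oxygen can attach to the rate alone (reading A) or to both parts (reading B). The last column joins the two parts with 'and', both off oxygen.

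| Breathless on self-care | Rate per min | Oxygen | As written, A | As written, B | With 'and' |
|---|---|---|---|---|---|
| No | ≥30 | on | met | not met | not met |
| No | ≥30 | off | met | met | not met |
| No | <30 | on | met | not met | not met |
| No | <30 | off | met | met | met |
| Yes | ≥30 | on | not met | not met | not met |
| Yes | ≥30 | off | not met | not met | not met |
| Yes | <30 | on | not met | not met | not met |
| Yes | <30 | off | **met** | **met** | not met |

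The last row is the defect, and it holds under either reading. With 'and', a breathless patient fails in all 4 of 4 combinations of rate and oxygen. Under reading A, a patient on oxygen who is not breathless also passes, and criterion v does not specify room air.

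**Step 2: does another criterion restore the requirement?**
- i and ii concern temperature and cough.
- iv is limited by its word 'other', which in sequence means other than the symptoms already named in i to iii.
- v measures saturation, not breathlessness.
- vi asks that the same state persist for 48 hours.
- vii concerns who assesses.
- viii requires every item but adds no content, and iii is already met.

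So a patient who is afebrile, has no or mild cough, no other symptom, SpO2 above 95% and a rate below 30 off oxygen, sustained for 48 hours, satisfies the text while still breathless.

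**Step 3: how often is the rate limit already met at entry?** Recovery needs a rate <30 and the severity marker is ≥30, so the two are complements. Exclusion, however, needs physician judgement plus at least two of three criteria. The patterns with fewer than two are: none met, rate alone, the saturation item alone, or the complication item alone. Oxygen for over one hour under the saturation item also counts under the complication item, so saturation alone drops out. A patient whose only severe sign is a rate of 30 or more is therefore not excluded by that rule. Most mild-to-moderate patients off oxygen probably start below 30, but the Protocol gives no distribution of baseline rates to confirm it.

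**Step 4: is the whole endpoint met at entry?** No. Inclusion requires "Typical clinical presentation of acute onset febrile illness with cough and a RT_PCR based laboratory confirmation test for COVID-19", so the temperature and cough criteria still have to be reached.

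**Step 5: conflict with a secondary outcome.** Absence of dyspnoea is timed from onset of illness and recovery from randomization, so the two must be compared by calendar date. As written, the recovery date can come before the date on which dyspnoea resolved.

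**The case against.** The strongest reply is that criterion iii is one item in a conjunction. A patient must also be afebrile, have at most mild cough, have no other attributed symptom, saturate above 95%, hold this for 48 hours and be judged by a blinded physician. Cough and saturation are respiratory items too, and they discriminate. Dyspnoea is reported separately, the same definition applies to both arms, and the trial is declared exploratory.

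Much of this stands, and it rules out several stronger readings that a reader might infer:

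- That a breathless patient simply counts as recovered. The patient can count, but only if every other criterion also holds.
- That the breathlessness part never decides anything. With a rate of 30 or more (or, under reading A, on oxygen), it is the only route through criterion iii.
- That the endpoint cannot register respiratory improvement. Criteria ii and v can.
- That breathlessness is the key symptom in this trial. The inclusion criteria name fever and cough and do not mention it.
- That the two uses of 30 per minute contradict each other. Below 30 and 30 or more are complements, so there is nothing to reconcile.
- That the wording favours one arm. Nothing in the document shows a differential effect.

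It can also be argued that criterion iv covers breathlessness if read as everything beyond the residual states tolerated in ii. The word 'other' points against that reading, and a primary endpoint should not depend on how each assessor takes it. Separate reporting of dyspnoea shows the discrepancy afterwards but does not correct the primary outcome.

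**Conclusion.** The concern holds in this form: the text of criterion iii does not require breathlessness to resolve, no other criterion restores that requirement, and both primary outcomes can therefore record recovery while the patient is still breathless on self-care. This conclusion rests on the wording alone and on no numerical assumption. That the rate limit is already met by most patients off oxygen at entry is a plausible inference, not a documented fact.

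The size cannot be derived from the document. If 20% to 40% of patients were breathless at entry (an assumption without support in the Protocol), the count would be 0.20 × 70 = 14 to 0.40 × 70 = 28 per arm. A reader might take that as the number misclassified. It is only a ceiling on an assumed share, because a patient is affected only if breathlessness outlasts every other criterion. The true number could be close to zero.

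The definition should be changed. It belongs to the Protocol's own primary endpoint, and the exploratory label does not remove the need for it to mean what it says, since section n still sets a significance level and expects meaningful conclusions.

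**What to change.** In criterion iii, replace 'or' with 'and', and make clear that both parts are assessed without supplemental oxygen. In criterion iv, drop the word 'other' and ask for absence of any symptom or sign attributed to COVID-19, apart from the mild residual symptoms that criterion ii allows.

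The cost is an edit to two lines. No new assessment is needed: symptoms and vital parameters are already monitored daily in hospital, and absence of dyspnoea is already a recorded timeline. Recovery dates will be somewhat later in both arms. The rate part will probably still add little in a mild-to-moderate population, but it will no longer be able to stand in for the absence of breathlessness.

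### The adjunct trial's definition of clinical recovery sets no room-air condition on SpO2 and no antipyretic condition on temperature, so a patient on support can be scored as recovered in both primary outcomes

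*Protocol*

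**What the plan says.** The adjunct-treatment synopsis has two primary outcomes: "Mean time (days) for clinical recovery", counted from randomization, and "Proportion of patients showing 'clinical recovery'". Both use one list of criteria under j. Efficacy. The relevant lines are:

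- **i (temperature):** "Normal body temperature (≤36.6°C axilla or ≤37.2 °C oral)".
- **ii (cough):** absent, or mild and, among other conditions, "relieved by minimal or no medication".
- **iii (breathing):** "Absence of breathlessness on routine daily self-care chore or respiratory rate less than 30 breaths per minute without supplemental oxygen".
- **v (saturation):** "Normalization of SpO2 by standard peripheral oximetry device (above 95 percent)".
- **vi (duration):** "Recovery should be sustained for at least 48 hours under physician observation".
- **vii:** the assessing physician is blinded to allocation.
- **viii:** "All of the above criteria ought to be fulfilled".

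A note below the list dates recovery from the first day on which the criteria are met.

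**The concern.** Temperature and SpO2 are both values that supportive treatment moves. If the definition does not say that they must be normal without that support, it can record the effect of the support as recovery. Criterion ii shows that the authors saw this problem for cough, where they limited medication, but there is no matching limit for fever. This matters for the whole trial population, because the first inclusion criterion requires an acute febrile illness. For oxygen, the only condition is in criterion iii, and its wording allows two readings.

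The date of recovery and the count of recovered patients in both arms are at stake. Two sites could also classify the same patient differently.

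**Working it through.** The plan gives no figure to reproduce here. The check is a joint reading of criteria i to viii, followed by a look at whether the situation can arise in this trial.

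**Step 1. Two readings of criterion iii.** Under the narrow reading, the off-oxygen phrase qualifies only the respiratory-rate limb that it follows. Under the wide reading, it qualifies both limbs. The narrow reading is the more natural one, but the grammar allows either.

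**Step 2. Two hypothetical patients, each stable for 48 hours with mild cough at most.**

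| Criterion | Patient A: on nasal oxygen, SpO2 97%, not breathless, no antipyretic | Patient B: no oxygen, temperature below the cut-off on regular antipyretics |
|---|---|---|
| i | met | met; antipyretics not addressed |
| ii | met | met |
| iii, narrow | met by the first limb | met |
| iii, wide | not met | met |
| iv | met, unless the assessor counts continuing oxygen need as a sign of illness | met |
| v | met; room air not required | met |
| vi | met | met |
| viii, all together | recovered (narrow), not recovered (wide) | recovered on either reading |

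The antipyretic gap has no counter-reading within the list. The oxygen gap depends on how iii is read.

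**Step 3. Can a patient be on oxygen in this trial?** At entry this is limited. Exclusion criterion i defines severe disease as at least two of three features. Oxygen support for over one hour appears in the second feature (with saturation at or below 93%) and again in the third. After entry it is possible. Time to supplemental oxygen is a listed secondary outcome, so such events are expected. The withdrawal note to Fig 1 concerns severe disease or severe complications needing critical, ICU or ventilator support, and does not name oxygen alone.

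**Step 4. Direction and size.** Adding conditions to a list that must be met in full can only delay a patient's recovery date or leave it unchanged. The present wording therefore dates recovery on the same day as the stricter wording, or earlier. Let f be the fraction of patients in whom a supported value was the last criterion outstanding, and d the days by which support brought it forward. The mean time to recovery is then understated by f × d. The document gives neither f nor d. Purely as assumptions:

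- f = 0.10, d = 2: 0.10 × 2 = 0.2 days.
- f = 0.30, d = 4: 0.30 × 4 = 1.2 days.

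These figures show the scale only and are not estimates for this trial. If f counted every patient on support, f × d would be an upper bound, since many would still be waiting on another criterion.

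The proportion recovered changes only for patients who meet the supported criteria but not the unsupported ones by the time the proportion is counted.

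**The case against.** The strongest reply is that the definition already excludes recovery on oxygen. Criterion viii makes iii mandatory, and on the wide reading iii bars anyone on oxygen, whatever v says. This stands in part: a reader might infer that every patient on oxygen is scored as recovered, and the document does not support that. It supports only that such a patient can be so scored. It is also fair that settling iii would by itself close the oxygen route, so the silence in v is the same gap seen from another line. Wording in v is still useful, because it fixes how the reading is taken.

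A second reply is that a blinded assessor could count continuing oxygen need under iv, and that the investigator may withdraw a patient for severity (m. Withdrawal Criteria). Both are possible, but both rest on judgement and neither touches the antipyretic gap.

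A reader might also infer that the open-label design turns this into bias between arms. Treating staff do know the allocation, and a blinded assessor would still record a supported value as normal, so the route exists. But the definition is common to both arms, the end-point assessment is blinded, and nothing in the document shows unequal use of oxygen or antipyretics. A 15-point gap in f with d = 3 would give 0.15 × 3 = 0.45 days between arms, but both inputs would be invented.

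Finally, this is a synopsis that refers to a fuller protocol, and measurement conditions may be stated there. The synopsis nevertheless sets the definition out in full, so any such condition belongs in it.

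**Conclusion.** The point holds in a limited form. Criterion i is silent on antipyretics, criterion v is silent on room air, and the off-oxygen condition in iii has an unclear scope. Followed as written, the definition can date recovery too early and can count a supported patient as recovered, in both primary outcomes. For fever this follows on any reading; for oxygen it follows on the more natural reading of iii. For an individual patient the error can only bring the date forward. Its size in the trial, and any difference between arms, cannot be derived from the document. The trial is declared exploratory and not statistically powered, which lowers the stakes for a formal claim but does not settle what the endpoint measures.

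**What to change.** Amend the definition in three places:

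1. In v, state that SpO2 is measured on room air.
2. In iii, reword so that the off-oxygen condition applies to both limbs.
3. In i, state that the temperature is normal without a recent antipyretic, with a window that the sponsor chooses and states.

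Then date recovery from the first day on which these unsupported values hold, keeping the 48-hour requirement of vi. These changes concern only when recovery is counted, not how patients are treated.

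The cost is small but not nil. Some recoveries will be dated later. The case record form must capture when oxygen stops and when antipyretics are given. The document does not show that it does: k. Medication covers recording of drugs for co-existent disease, and the secondary outcomes list the time to supplemental oxygen but not its end. The sponsor should confirm or add these fields.

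### Adjunct trials: the viral-clearance swab day is set by the patient's own recovery, which biases that comparison against a faster-recovering arm; the secondary timelines start at illness onset and not at randomisation

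*Protocol*

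**What the plan says.** The point concerns section j (Efficacy) of the adjunct-treatment protocol, which is common to the three formulation trials.

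- **Primary outcome.** Time to clinical recovery is measured as "Day of randomization to the day of clinical recovery". The criteria add that "Recovery should be sustained for at least 48 hours under physician observation", and a note dates recovery back: "Clinical recovery would be deemed from the first day of satisfying the above criteria".
- **Secondary outcome 1.** "Rate of patients with negative SARS-CoV-2 on nasal or throat swab in a 2 day continuous real time RT-PCR test". The test begins on the first day of clinical recovery or on "Day 10 after onset of symptoms depending on whichever of the two time points is first achieved". The outcome is a proportion at a day that varies by patient, not a time to event.
- **Secondary outcome 2.** "Timelines (days counted from onset of illness)- normal body temperature", followed by a long list that includes pneumonia, supplemental oxygen, steroid use, intensive care, ventilation and death.
- **Secondary outcome 3.** The proportion of patients with such events: "the events are similar to those listed under Timelines, see above".

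The inclusion criteria (section i) require a symptomatic, RT-PCR-confirmed illness at entry. They set no upper limit on days since onset. The statistical statement (section n) predefines a two-sided p<0.05 and applies the comparison to primary and secondary measures.

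**The concern.** Outcome 1 is measured on a day that treatment can move. If the adjunct shortens recovery, its patients reach the trigger sooner and are swabbed when fewer people, treated or not, have cleared the virus. The difference in proportions then mixes drug effect with swab timing, and randomisation does not protect against that. A later analysis cannot repair it, because a swab on a common day was never taken.

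Two lesser problems concern the time origin. Day 10 of illness can fall on or before randomisation for a patient enrolled late, and treatment cannot affect that result. Outcome 2 uses a different clock from the primary outcome, and nothing stated limits outcomes 2 and 3 to events that arise after randomisation.

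**Working it through.** The protocol states no clearance rate, recovery time or effect size for the adjunct trials, so there is no figure to reproduce. Only the 70 patients per arm, the two-sided 0.05 level and the swab-day rule come from the protocol. Every other input below is an assumption.

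**1. Size of the swab-day bias with no viral effect.** Let F(t) = 1 − exp(−ln2 · (t/m)^k) be the proportion negative by illness day t, with m = 12 days and k = 2.

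- Extreme case, with every patient in one arm swabbed on day 7 and every patient in the other on day 10: F(7) = 0.21, F(10) = 0.38, a gap of 17 points. Over m = 10 to 20 and k = 1.5 to 2, this gap runs from 8 to 21 points.
- With patient-level spread: recovery day R is log-normal (sigma 0.30 or 0.45), the swab day is min(R, 10), and the proportion negative is the average of F(min(R, 10)).

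| Median recovery, illness day | Sigma | Faster arm | Slower arm | False deficit |
|---|---|---|---|---|
| 7 vs 10 | 0.30 | 22.3% | 32.5% | 10.2 points |
| 7 vs 10 | 0.45 | 22.4% | 30.5% | 8.2 points |
| 11 vs 14 | 0.30 | 34.4% | 37.2% | 2.8 points |
| 11 vs 14 | 0.45 | 32.2% | 35.5% | 3.2 points |

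The last two rows are small because most patients in both arms reach the day-10 cap first.

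**2. Attenuation or reversal.** This is a separate simulation with other assumptions. Control medians from randomisation are 6 days to recovery and 7 days to clearance (log-normal, sigma 0.45). Mean onset-to-randomisation is 3, 5 or 7 days, and the recovery–clearance correlation is 0, 0.5 or 0.8. Differences are treated minus control, in points.

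| Treated arm | Protocol's swab day | Fixed day 7 after randomisation |
|---|---|---|
| Recovery 20% or 30% faster, clearance unchanged (18 scenarios) | −2.5 to −15.9 | 0 |
| Recovery 30% faster, clearance 10% faster (9) | −1.5 to −12.6 | about +9 |
| Recovery 30% faster, clearance 15% faster (9) | −9.7 to +0.3 | about +14 |
| Both 30% faster (9) | +4.9 to +9.0 | about +29 |

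For scale, 70 per arm has 80% power only for differences of about 19 to 23 points (control proportions 0.3 to 0.7).

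**3. Day 10 before entry.** In the same simulation, the swab day falls on or before randomisation in about 4% of patients when mean onset-to-randomisation is 5 days, and in about 17% when it is 7 days.

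**4. Onset clock: noise.** If the interval before randomisation (SD s) is independent of the time after it (SD 3 days), the total SD is √(3² + s²). Power for a 1.5-day effect is Φ(1.5 / (SD · √(2/70)) − 1.96).

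- s = 0: SD 3.00, power 84%
- s = 2: SD 3.61, power 69%
- s = 3: SD 4.24, power 55%
- s = 4: SD 5.00, power 43%

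If patients enrolled later also recover sooner after entry, the covariance is negative and the loss is smaller.

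**5. Events already present.** With post-randomisation risks of 20% versus 10% (ratio 0.50) and a share q already having the event in both arms, the ratio becomes (q + (1 − q)·0.10) / (q + (1 − q)·0.20).

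- q = 0.1: 0.19/0.28 = 0.68
- q = 0.2: 0.28/0.36 = 0.78
- q = 0.3: 0.37/0.44 = 0.84

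The ratio moves towards 1 but does not cross it.

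**The case against.** The best case for the plan is that the trials are labelled exploratory and unpowered, the primary outcome uses the right clock, and viral clearance does not rest on outcome 1 alone. Outcome 2 lists time to a negative swab, and the study flow diagram schedules PCR at weeks 4, 8 and 12. This limits the severity. It does not repair outcome 1: those PCRs do not define it, and the diagram lets the week 4 or week 8 evaluation be skipped within two weeks of discharge.

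Several stronger readings are tempting, and the documents do not support them:

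- *A drug that speeds recovery will look worse.* This holds only if recovery accelerates clearly more than clearance. If both improve equally, the benefit is shrunk and keeps its sign.
- *The false deficit is 17 points.* That needs every patient in an arm to be swabbed on one exact day.
- *A recovery-day swab cannot be scheduled, because recovery is confirmed only after 48 hours.* Inpatients are assessed daily, so a swab can be taken provisionally when the other criteria are first met and kept if recovery holds.
- *The onset clock biases against the drug.* The interval before randomisation is balanced between arms in expectation.
- *Any listed event could predate entry.* The criteria require an acute febrile presentation and exclude severe disease and patients likely to need intensive care or ventilation. Death cannot precede randomisation. The exposure is to items such as pneumonia, steroid use or brief oxygen.

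Handling of events present at baseline could also be left to an analysis plan. The swab day and the time origin are fixed here.

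**Conclusion.** The concern stands in limited form. Outcome 1 ties the swab day to the primary outcome and so biases the viral-clearance comparison against the faster-recovering arm. The direction of the bias follows from the text, provided the proportion negative rises with time since infection. Its size rests wholly on assumptions: about 8 to 10 points where most patients in the faster arm recover before day 10, and about 3 points where the day-10 cap governs most patients. The onset clock in outcome 2 costs precision, and pre-entry events in outcomes 2 and 3 dilute effects; neither changes the direction. The change should be made, but these are secondary outcomes of an exploratory design and the primary outcome's clock is sound.

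**What to change.** (a) Start every secondary timeline at randomisation, count only events that are new after randomisation, and adjust for days from symptom onset to randomisation as a baseline covariate. This costs nothing beyond wording.

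(b) Redefine outcome 1 with all randomised patients as the denominator. The numerator is those RT-PCR negative on both of two consecutive days, starting on one prespecified day after randomisation that is the same in both arms and independent of recovery. The cost is that patients discharged before that day need two return or home swabs, and some of these will be missed, so the protocol should state how missing swabs count.
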